## STATEMENT OF COMPLIANCE

The trial will be conducted in accordance with International Conference on Harmonisation Good Clinical Practice (ICH GCP) and the applicable United States (US) Code of Federal Regulations (CFR). The Principal Investigator will assure that no deviation from, or changes to the protocol will take place without prior agreement from the sponsor and documented approval from the Institutional Review Board (IRB), except where necessary to eliminate an immediate hazard(s) to the trial participants. All personnel involved in the conduct of this study have completed Human Subjects Protection and ICH GCP Training.

The protocol, informed consent form(s), recruitment materials, and all participant materials will be submitted to the IRB for review and approval. Approval of both the protocol and the consent form must be obtained before any participant is enrolled. Any amendment to the protocol will require review and approval by the IRB before the changes are implemented to the study. All changes to the consent form will be IRB approved; a determination will be made regarding whether a new consent needs to be obtained from participants who provided consent, using a previously approved consent form.

## 1 PROTOCOL SUMMARY

### 1.1 SYNOPSIS

**Title of the Study:** Endoscopic Trigger Finger Release

**Number of Subjects:** 24

**Objective:** The objective of this study is to compare recovery, scar and patient satisfaction after retrograde endoscopic trigger finger release versus standard open surgical treatment.

**Methodology:** Consecutive patients presenting with trigger finger interested in surgical release of the A1 pulley will be prospectively treated with endoscopic versus open surgical release of the A1 pulley. Study measures will include scar assessment based on the Patient and Observer Scar Assessment Scale (POSAS) administered at 1 week, 1 month, and 6 months post-operatively, overall satisfaction (scale of 1 to 10), days before return to work, duration of post-operative occupational therapy, pain medication use, operative time, and complication and recurrence rates..

**Visit Schedule:** Pre-operative visit, post-operative visits at 1 week, 1 month, and 6 months post-operatively.

**Diagnosis and Main Inclusion Criteria for Inclusion/Exclusion:** Subjects with diagnosis of trigger finger.

**Inclusion Criteria:**

- Male or Female >18 years of age
- Trigger finger, recommended for surgical release
- Be in good health other than the trigger finger
- Have realistic expectations of surgical results
- Understand and be willing to follow all aspects of the study protocol and have signed and dated the IRB-approved Informed Consent Form and the Authorization for Use and Release of Health and Research Study Information (HIPAA) form prior to any study-related procedures being performed

**Exclusion Criteria: To be eligible for enrollment, the subject must not:**

- Have collagen-vascular, connective tissue, or bleeding disorders
- Be a smoker or have smoked in last 2 months
- Have any disease, including uncontrolled diabetes, which is clinically known to impact wound healing ability
- Have regional sympathetic dystrophy
- Be pregnant, lactating or expecting to be within the next 24 months
- Currently have an alcohol/substance abuse problem or have had a relapse within one year to screening visit
- Have an abscess or infection at the time of surgery
- Have a condition or be in a situation that, in the Investigator's opinion, may put the subject at significant risk, may confound the study results, or may interfere significantly with the subject's participation in the study

**Duration of the Study:** Subjects will be followed for 6 months post release of the A1 pulley.

**Criteria for Evaluation:** Primary outcome measures include scarring based on Patient and Observer Scar Assessment Scale (POSAS) scores administered 1 week, 1 month, and 6 months post-operatively between patients treated with endoscopic versus open surgical release of the A1 pulley. Secondary outcome measures include overall satisfaction (scale of 1 to 10), days to return to work, duration of post-operative occupational therapy, pain medication use as well as complication and recurrence rates between the two treatment groups.

**Statistical Methods:**

[figure not shown]
Sample size calculation: Total POSAS scores range from 12 to 120. Though the POSAS has not been used to assess scarring after trigger finger release, the tool is validated with high internal consistency and reliability.

A total of 24 patients (12 in the endoscopic arm and 12 in the standard open arm) will provide sufficient information to produce descriptive summaries of study outcome endpoints and to perform exploratory analyses.

The purpose of this study is to compare scar and recovery after retrograde endoscopic trigger finger release versus standard open surgical treatment. We hypothesize that patients treated with the retrograde endoscopic approach will have improved scarring compared to patients treated with the open approach, based on POSAS scores. We also hypothesize that the patients in the endoscopic treatment arm will have a faster recovery (return to work sooner with fewer days of occupational therapy), have higher overall satisfaction (scale 1 to 10) and use less pain medication. We anticipate that the two treatments will not differ significantly in complication or recurrence rate.

**Schedule of Visits and Procedures:** As depicted in Section 1.2.

## 1.2 SCHEMA

## 2 INTRODUCTION

### 2.1 ABBREVIATIONS AND TERMS:

OT Occupational therapy

POSAS Patient and Observer Scar Assessment Scale

### 2.2 BACKGROUND AND CLINICAL RATIONALE FOR DATA REVIEW

Trigger finger is an entrapment tendinopathy in which the flexor tendon catches within a thickened or narrowed A1 pulley with flexion and extension of the digit. Patients present with complaints of pain, snapping, or locking of the finger at the MCP joint. With an incidence between 2 and 3% in the general population, trigger finger is one of the most common causes of disability and pain in the hand.

Initial treatment is conservative and nonsurgical management includes: non-steroidal anti-inflammatory drugs, activity modification, splinting, and corticosteroid injections. Though some relief may be noted initially, the reported recurrence rate after corticosteroid treatment is up to 48%. Definitive treatment often requires release of the A1 pulley through an open, percutaneous, or endoscopic surgical technique. In the open approach, an incision is made in the palm - most commonly at the distal palmar crease - which causes great discomfort to patients. The endoscopic approach reported by Pegoli and colleagues requires two incisions: one at the proximal interphalangeal crease and one in the mid palm. The percutaneous approach avoids use of these painful palmar incisions, but concerns exist over the safety of this blind technique. As such, techniques currently available for the surgical treatment of trigger finger fall short in one of two ways: 1) they require an incision of the palm, which can be painful and unsightly to patients or 2) the release is performed blindly.

## 3 STUDY OBJECTIVES

The objective of this study is to compare scar and recovery after retrograde endoscopic trigger finger release versus standard open surgical treatment.

## 4 STUDY DESIGN

### 4.1 OVERALL DESIGN

Consecutive patients (until 12 patients are enrolled in each treatment arm) presenting with trigger finger interested in surgical release of the A1 pulley will be offered participation in the study. Additional subjects may be enrolled, as needed to achieve 12 patients in each treatment arm, in the event of patient death or withdrawal from the study. Once enrolled, they will be treated with one of two techniques: endoscopic versus open surgical release. Study measures will include scar assessment based on the Patient and Observer Scar Assessment Scale (POSAS) administered at 1 week, 1 month, and 6 months post-operatively, overall satisfaction (scale of 1 to 10), days before return to work, duration of post-operative occupational therapy, pain medication use, operative time, and complication and recurrence rates.

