#### 4.2 STUDY STRUCTURE

This is a prospective clinical trial, as the participants will be treated, after enrollment, with endoscopic versus open release.

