#### 4.5 VISITS & PROCEDURES

Patients will undergo endoscopic or open treatment. Follow-up assessments will be performed at 1 week, 1 month, and 6 months post-operatively.

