### 5.3 INCLUSION CRITERIA

- Male or Female >18 years of age
- Trigger finger, recommended for surgical release
- Be in good health other than the trigger finger
- Have realistic expectations of surgical results
- Be willing to undergo treatment based on the treatment arm to which they are randomized
- Understand and be willing to follow all aspects of the study protocol and have signed and dated the IRB-approved Informed Consent Form and the Authorization for Use and Release of Health and Research Study Information (HIPAA) form prior to any study-related procedures being performed

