## 10 STUDY ADMINISTRATION PROCEDURES

### 10.1 SUBJECT ENTRY PROCEDURES

#### 10.1.1 OVERVIEW OF ENTRY PROCEDURES

Prospective subjects as defined by the criteria in Section 5.3 and 5.4 (inclusion/exclusion criteria) will be considered for entry into this study.

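### Section 5.3 refers to randomized arms, but the visible design, entry and consent text gives no random assignment step, concealment or timing, and would permit choice of technique

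*Combined protocol and SAP*

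**What the plan says.** **Where randomization appears.** Section 5.3 requires each subject to "Be willing to undergo treatment based on the treatment arm to which they are randomized". Section 10.1.1 makes this binding, since prospective subjects "as defined by the criteria in Section 5.3 and 5.4 (inclusion/exclusion criteria) will be considered for entry into this study". The inclusion list in the synopsis omits the criterion.

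**Where assignment would be expected.**
- Synopsis, Methodology: consecutive patients "will be prospectively treated with endoscopic versus open surgical release of the A1 pulley".
- 4.1: "Once enrolled, they will be treated with one of two techniques: endoscopic versus open surgical release".
- 4.2: "This is a prospective clinical trial, as the participants will be treated, after enrollment, with endoscopic versus open release". The word randomized is not used.
- 4.5: "Patients will undergo endoscopic or open treatment".
- 6.1.1 and 6.1.2: enrollment is the signing of consent and HIPAA forms; history, examination and photographs are listed, but no allocation.
- 10.1.2: consent leads to an ascending subject number, tied to no allocation list.
- 10.2: eligible subjects are counseled on the available techniques; how an arm follows is not stated.

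**Fill and replacement.** Section 4.1 enrolls "Consecutive patients (until 12 patients are enrolled in each treatment arm". Sections 4.1, 5.1 and 9.6 allow extra subjects to restore 12 per arm after death or withdrawal.

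**The concern.** The study exists to compare two techniques (3). It has a directional hypothesis favoring the endoscopic arm (9.3), a sample size set for a 10-point POSAS difference (9.6), and between-arm t-tests with no stated adjustment for baseline factors or surgeon (9.5). More than one surgeon treats (4.4, 10.2).

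If technique is chosen rather than randomly assigned, the arms can differ in age, digit, occupation or surgeon before any incision is made. The exclusions in 5.4 remove some causes of poor healing but none of these. The primary analysis is descriptive (9.3.1), which does not help: a described difference between non-comparable arms is as confounded as a tested one. Assignment also cannot be repaired once subjects have been treated.

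**Working it through.** **1. Does the text determine how an arm is assigned?** Take three ways a site might work and hold each against the visible text.

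| Method at the site | Synopsis, 4.1, 4.2, 4.5, 5.1 | 6.1, 10.1.2, 10.2 | 5.3 |
|---|---|---|---|
| Concealed random list | compatible | compatible | compatible |
| Alternation | compatible | compatible | conflicts |
| Surgeon or patient chooses | compatible | compatible | conflicts |

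Only the entry criterion separates the first row from the others, and it describes what the subject must accept, not what the site must do. On timing, 4.1 and 4.2 put treatment after enrollment. Nothing says when the arm is assigned or disclosed relative to consent and the eligibility check.

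**2. The plan's own sample size.** Inputs from 9.6: difference 10, SD 8, two-sided 5%, power 80%, equal arms.
- Normal approximation: n = 2 × (1.960 + 0.842)² × 8² / 10² = 10.05, so 11 per arm.
- Two-sample t-test: 11.09, so 12 per arm. The stated figure is reproduced.
- Power at 12 v 12 (noncentrality 1.25 × √(12 × 12 / 24) = 3.06, 22 df): 83.3%.

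**3. Places forced by the 12-per-arm rule.** If one arm fills when the other holds k subjects (k = 0 to 11), the remaining 12 − k places can go only to the open arm. So at least 1 is forced, whatever the method. The documents name no scheme, so two are assumed as a range.
- Random permutation of 12 and 12: P(k) = 2 × C(11+k, k) / C(24, 12). Mean forced = 24/13 = 1.8 of 24; P(2 or more) = 0.48; P(4 or more) = 0.09.
- Fair coin until one arm is full: P(k) = 2 × C(11+k, k) × 0.5^(12+k). Mean forced = 3.9 of 24; P(2 or more) = 0.83; P(4 or more) = 0.50.

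For replacements: if all open vacancies are in one arm, the next subject's arm is known. If both arms have vacancies, it is not.

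**4. What forced places could do.** This is an illustration only. Suppose there is no true effect and every forced place goes to a subject whose expected POSAS is 10 points better. That shift is an assumption with no source in the documents. The open arm's mean then moves by 10s/12 for s such places. The simulated rejection rate of the 5% t-test is:

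| s | Shift in arm mean (points) | SD 8 | SD 11 |
|---|---|---|---|
| 1 | 0.8 | 5.0% | 4.9% |
| 2 | 1.7 | 6.3% | 5.7% |
| 4 | 3.3 | 12.4% | 9.2% |

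Rows 2 and 4 sit near the two means in step 3. A smaller assumed shift would do less.

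**5. Power if arms may end unequal.** The noncentrality becomes (10/SD) × √(n₁n₂/24).
- SD 8: 83.3% at 12 v 12; 83.0% at 11 v 13.
- SD 11 (top of the range in 9.6): 56.7% and 56.4%.

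**The case against.** **Randomization is stated, and part of the document is unseen.** The 5.3 criterion reads most naturally as agreement to an arm not yet known. The 1.2 schema, one synopsis figure, some opening pages and the consent form were not visible. A reader might infer that the trial is not randomized; the documents do not support that, since 5.3 says otherwise and a diagram could show a randomization node. This stands and limits the claim to unspecified and inconsistent assignment. A node alone would not supply concealment, timing or a replacement rule.

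**Enrollment is consecutive.** The synopsis, 4.1 and 5.1 all say so. That limits who can be steered into a known place. It does not remove the scope, because candidates are identified in advance from the appointment calendar (6.1), and it does nothing about choice of technique once a patient has enrolled.

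**The quota is minor.** This largely stands. A reader might infer that every replacement's arm is known, or that the quota alone distorts the test. The first holds only when all vacancies are in one arm, and replacement is optional in the text. The second depends on the assumed scheme and on an unsourced 10-point shift; one steered place leaves the error rate at about 5%.

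**Consent before screening.** A reader might also fault this order (6.1.1, 6.1.2). It follows from the rule that consent precede study procedures and is not a defect.

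**The study is descriptive and exploratory** (synopsis Statistical Methods, 9, 9.3.1, 9.5). This is true of the analyses. But the objective and hypotheses are comparative and 9.6 says the trial is powered, so comparability of the arms still matters.

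**Conclusion.** The point holds as an inconsistency and an omission. Section 5.3 presupposes randomization, while the visible design, entry, consent and compliance sections describe no random assignment, concealment or timing, and would accommodate choice by surgeon or patient. Under that reading, a difference in scar or recovery could not be attributed to technique with confidence. The size of the bias cannot be derived from the documents, because it depends on how technique is in fact assigned.

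The fill-and-top-up rule is a secondary weakness. At least 1 of 24 assignments is always forced, with a mean of about 1.8 to 3.9 under the two assumed schemes. Knowing those places in advance also requires that arm counts be visible to recruiters, which is an inference from the unmasked surgery. The rule does not carry the conclusion; the unspecified assignment of all 24 does. The matter should be settled before enrollment.

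**What to change.** **If randomization is intended:**
- In the synopsis, 4.1, 4.2 and 5.1, state 1:1 randomization from a computer-generated concealed list held by someone not involved in recruitment or surgery. Add the 5.3 criterion to the synopsis list. The block scheme is for the trial statistician to choose.
- In 6.1 and 10.1.2, add the step: the next concealed allocation is opened after written consent and confirmed eligibility, and before surgery.
- Make the list longer than 24. Replace the stopping rule of 12 enrolled in each arm with enrollment until 24 subjects are randomized.
- In 4.1, 5.1 and 9.6, give any replacement the next concealed allocation rather than the arm that lost a subject.
- Check that the schema and the consent form say the same.

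**If it is not intended:** delete the randomization wording from 5.3, state how technique is assigned, call the study a non-randomized comparison, report baseline factors and surgeon by arm, and limit conclusions to association.

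**Cost:** one amendment with IRB approval and, if randomized, one list. Planned N stays 24. Arms may end slightly unequal; at 11 v 13 the loss of power is 0.3 percentage points at either SD (83.3% to 83.0% at SD 8; 56.7% to 56.4% at SD 11).

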#### 4.2 STUDY STRUCTURE

This is a prospective clinical trial, as the participants will be treated, after enrollment, with endoscopic versus open release.

#### 4.3 DURATION

Subjects will be followed for 6 months post-operatively. POSAS scores will be obtained at 1 week, 1 month, and 6 months post-operatively. These scores along with measures of pain medication use, days before return to work, and duration of OT will be obtained from each subject during their post-operative visit. Complication and recurrence rates will also be noted at each post-operative visit. Study visits will coincide with standard clinical course visits.

#### 4.4 STUDY QUESTIONNAIRES/ASSESSMENT

The patients of [name], [name], [name], and [name] eligible to participate in the study will proceed with baseline assessments once study consents have been signed and the patient has been enrolled in the study.

#### 4.5 VISITS & PROCEDURES

Patients will undergo endoscopic or open treatment. Follow-up assessments will be performed at 1 week, 1 month, and 6 months post-operatively.

### 5 STUDY POPULATION CHARACTERISTICS

### 5.1 NUMBER OF SUBJECTS

Consecutive patients presenting with trigger finger interested in surgical release of the A1 pulley will undergo endoscopic versus open surgical release of the A1 pulley. A total of 12 subjects are to be enrolled for each treatment arm. Additional subjects may be enrolled, as needed to achieve 12 patients in each treatment arm, in the event of patient death or withdrawal from the study.

### 5.2 STUDY POPULATION CHARACTERISTICS

Subjects who meet the inclusion/exclusion criteria detailed below will be enrolled into the study.

### 5.3 INCLUSION CRITERIA

- Male or Female >18 years of age
- Trigger finger, recommended for surgical release
- Be in good health other than the trigger finger
- Have realistic expectations of surgical results
- Be willing to undergo treatment based on the treatment arm to which they are randomized
- Understand and be willing to follow all aspects of the study protocol and have signed and dated the IRB-approved Informed Consent Form and the Authorization for Use and Release of Health and Research Study Information (HIPAA) form prior to any study-related procedures being performed

### 5.4 EXCLUSION CRITERIA PROCEDURES

- Have collagen-vascular, connective tissue, or bleeding disorders
- Be a smoker or have smoked in last 2 months
- Have any disease, including uncontrolled diabetes, which is clinically known to impact wound healing ability
- Have regional sympathetic dystrophy
- Be pregnant, lactating or expecting to be within the next 24 months
- Currently have an alcohol/substance abuse problem or have had a relapse within one year to screening visit
- Have an abscess or infection at the time of surgery
- Have a condition or be in a situation that, in the Investigator's opinion, may put the subject at significant risk, may confound the study results, or may interfere significantly with the subject's participation in the study

## 6 VISITS & PROCEDURES

### 6.1 PRE-SCREENING & VISITS

The physician's appointment calendar will be pre-screened of potential study candidates who would be eligible for surgical treatment. No study related data will be collected/administered until patient has signed consent and HIPAA.

#### 6.1.1 PROCEDURES FOR FINAL STUDY ENTRY

A subject is considered "enrolled" when he/she has signed the IRB-approved consent form and HIPAA authorization in the presence of the Investigator, who will then collect and record the subject's demographic information and medical history.

#### 6.1.2 PRE-OPERATIVE VISITS

The subject will be screened in accordance with the inclusion/exclusion criteria, medical history will be collected, a physical exam will be performed and medical photography will be obtained, as is the standard of care.

#### 6.1.3 FOLLOW-UP VISITS

Subjects will be required to attend post-operative visits at 1 week, 1 month, and 6 months post-operatively, as is the standard of care. Review of medical history and physical examination will be conducted at all post-operative visits. At 1 week, 1 month, and 6 months post-operatively, pain medication use, days before return to work, duration of occupational therapy, as well as POSAS scores will be obtained and photos will be taken.

### 6.2 STANDARD AND RESEARCH PROCEDURES

All evaluations, procedures performed, and information obtained during pre-operative and post-operative visits will be within the standard of care with the exception of the POSAS questionnaire. The POSAS questionnaire contains a Patient Scale to be completed by the patient and an Observer Scale to be completed by the patient's surgeon-of-record. The Patient Scale is comprised of 6 questions regarding pain, itching, color, stiffness, thickness, and irregularity of their scar scored

numerically from 1 to 10. There is a 7th question, also on a scale of 1 to 10, that asks the patient for their overall opinion of the scar.

The POSAS questionnaire will be completed by patients at 1 week, 1 month, and 6 months post-operatively. In an effort to minimize inconvenience and avoid undue stress to the subjects, they will be given unlimited time to complete the questionnaire and will be allowed to skip questions as desired.

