## 9 STATISTICAL PROCEDURES

Every attempt will be made to collect complete data and limit the occurrence of missing data. Due to the descriptive nature of all analyses, no imputation of missing data will be performed. Descriptive summaries will be based on all observations available within each of the relevant analysis populations.

Descriptive statistics will be presented for key outcome measures.

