#### 9.3.1 PRIMARY OUTCOME MEASURE ANALYSIS

Primary outcome measures of POSAS scores at 1 week, 1 month, and 6months post-operatively will be analyzed using descriptive statistics, including n, mean, standard deviation, median, minimum, maximum, and skewness.

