## 9.5 EXPLORATORY ANALYSES

POSAS scores at 1 week, 1 month, and 6 months post-operatively will be analyzed between patients treated with endoscopic versus open release using 2-sample t-tests. Differences in pain medication use, days before return to work, duration of OT, operative time, overall satisfaction, complication and recurrence rates between patients treated with endoscopic versus open surgical release of the A1 pulley will be tested for significance using 2-sample t-tests. Additional analyses of possible relationships between outcomes may also be performed using appropriate inferential tests.

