## 9.6 SAMPLE SIZE CALCULATION

Total POSAS scores range from 12 to 120. Though the POSAS has not been used to assess scarring after trigger finger release, the tool is validated with high internal consistency and reliability.

The trial will be powered to detect a difference in POSAS score of 10, deemed to be clinically significant by the investigators. The POSAS standard deviations in studies previously published on carpal tunnel release and carotid endarterectomies ranges from 1.0 to 11.0. To detect a mean difference in POSAS score of 10 points (SD = 8) with a two-sided significance level of 5% and power of 80% with equal allocation to two arms would require 12 patients in each arm of the trial. Additional subjects may be enrolled, as needed to achieve 12 patients in each treatment arm, in the event of patient death or withdrawal from the study.

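### Does the plan need a scoring rule for POSAS forms on which the patient has skipped items?

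*Combined protocol and SAP*

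**What the plan says.** All references are to the combined protocol and SAP.

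- Section 6.2 describes the patient part of the instrument: "The Patient Scale is comprised of 6 questions regarding pain, itching, color, stiffness, thickness, and irregularity of their scar scored" from 1 to 10, plus a seventh question on overall opinion. The surgeon-of-record completes the Observer Scale. Patients have unlimited time and "will be allowed to skip questions as desired".
- Section 9 states that "no imputation of missing data will be performed", giving the descriptive nature of the analyses as the reason. It adds: "Descriptive summaries will be based on all observations available" in each analysis population.
- Section 9.3.1 says the primary POSAS scores "will be analyzed using descriptive statistics, including n, mean, standard deviation" and other summary measures. Section 9.5, headed as exploratory, says the scores at each visit "will be analyzed between patients treated with endoscopic versus open release using 2-sample t-tests".
- Section 9.6 says "Total POSAS scores range from 12 to 120" and sizes the trial for a difference of 10 points with SD 8. Extra enrolment is allowed "in the event of patient death or withdrawal from the study".

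No section sets a minimum number of answered items or says what happens to the total when one is blank.

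**The concern.** The protocol expressly permits blank items, the trial is sized on a summed score, and nothing links the two. An incomplete form could be handled in two ways that both appear to comply:

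- **Sum what was answered.** The total is then too low by the unrecorded value, 1 to 10 points per skipped item. If lower is better, as items such as pain and itching suggest, the scar looks better than it is. For one patient the shift could equal the whole 10-point target difference.
- **Treat the total as missing.** Extra enrolment covers death and withdrawal only, so a lost total is not made up, and 12 per arm leaves little slack.

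Two analysts could then report different primary means from the same forms, and the comparison between arms could lose power. A sentence or two in Section 9 would seem a cheap cure.

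**Working it through.** **Inputs.** Difference 10, SD 8, two-sided 5%, 80% power, equal arms of 12 (Section 9.6). Six patient items scored 1 to 10 (Section 6.2). A range of 12 to 120 implies 12 items, hence six observer items (an inference). The skip permission covers patients only, and the seventh question lies outside the total, so six items are at risk per form. The documents give no skip rate, so those below are assumptions.

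**1. The plan's own figure.** Normal approximation: n per arm = 2 × (1.960 + 0.842)² × (8/10)² = 10.05, rounded up to 11. The two-sample t-test with the noncentral t distribution gives 11.09, rounded up to 12. The stated 12 per arm reproduces.

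**2. Power if incomplete totals are missing.** The noncentrality is 10 / (8 × √(1/n₁ + 1/n₂)).

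| Complete totals per arm | Noncentrality | Power |
|---|---|---|
| 12 and 12 | 3.06 | 83.3% |
| 12 and 11 | 2.99 | 81.5% |
| 11 and 11 | 2.93 | 79.6% |
| 12 and 10 | 2.92 | 79.3% |

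**3. How many totals might be lost.** Let q be the skip rate per item. If items are skipped independently, the chance that a total is missing is 1 − (1 − q)⁶. If skipping is clustered, so that a patient who skips leaves three of six items blank, the chance is 6q/3 = 2q. Power is averaged over binomial numbers of complete totals in each arm of 12.

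| q | Missing, independent | Power | Missing, clustered | Power |
|---|---|---|---|---|
| 1% | 5.9% | 80.6% | 2% | 82.4% |
| 2% | 11.4% | 77.6% | 4% | 81.5% |
| 5% | 26.5% | 68.0% | 10% | 78.4% |

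Average power falls to 80% at about 7% missing, or 0.07 × 24 = 1.7 forms.

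**4. Size of the partial-sum error.** One patient in 12 skipping one item moves that arm's mean by 1/12 = 0.08 to 10/12 = 0.83 points, against a target of 10. A bias between arms needs skipping to differ by arm: at 5% against 0%, with items scored 5, it is 6 × 0.05 × 5 = 1.5 points.

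**5. Would scaling up help?** Take as an example a rule that uses the mean of the answered items times six when at least five of six are answered. Under independent skipping, the chance of two or more blanks is 1 − (1 − q)⁶ − 6q(1 − q)⁵ = 0.1%, 0.6% and 3.3% for the three rates. Power is then 83.2%, 83.0% and 81.8%, if scaled totals keep the same SD. Under clustered skipping every patient who skips has three blanks and fails the minimum, so power stays at 82.4%, 81.5% and 78.4%. The gain is nil.

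**6. Which reading the text supports.** A partial sum gives a blank item the value 0, which is not on the 1-to-10 item scale. In substance that fills in a value, which Section 9 says will not be done. The result also no longer lies on the 12-to-120 scale of Section 9.6: one blank makes the range 11 to 110. Leaving the total missing fills in nothing and uses every total that exists. Section 9 also still allows the answered items to be summarised.

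**The case for a change.** The strongest case for a change is that Section 9 does not define an observation at item or form level. Adding up the answered items also uses everything available, and an analyst could say that no value was filled in. The mean and SD in Section 9.3.1 are themselves the primary result, so the rule affects the reported result even without a formal test. Section 9.6 does speak of powering the trial, and two unusable totals take power just under 80%. A rule is best chosen before anyone sees which arm skipped more.

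Part of this stands. The rule is not written down, and a sentence saying that a total with any skipped patient item is missing, with counts by arm and visit, would do no harm. It would record what a careful analyst would do anyway. The rest is weaker. The two readings are not equally plausible, for the reasons in step 6. The power argument relies on assumed skip rates for a short form with unlimited time, and Section 9 commits to every attempt at complete data. The t-tests are exploratory, and the synopsis justifies 24 patients as enough for descriptive summaries and exploratory work. Scaling up is a matter of judgement: it assumes that a skipped item resembles the same patient's other answers, although the items mix pain, itching, color and thickness.

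**Conclusion.** No change is needed. The plan leaves a detail unstated, and its own statements lead an analyst to a sensible default: a form with a skipped patient item has no total, and the answered items can still be summarised. With difference 10 and SD 8, the cost is 83.3% − 81.5% = 1.8 percentage points of power for one lost total, and 83.3% − 79.6% = 3.7 points for one lost from each arm. The largest loss shown, to 68.0%, needs independent skipping at 5% on every item, which nothing in the documents supports. The assumed SD matters more than a few lost totals: at 11, the top of the range quoted in Section 9.6, power with complete data is 56.7%. Replacing the no-imputation choice with scaled totals is a trade-off on which statisticians can reasonably differ, and its benefit depends on an unknown pattern of skipping. This conclusion rests on the primary analysis remaining descriptive and on skipping being infrequent. If blanks proved common or clearly different between arms, the number of missing totals by arm and visit would have to be shown beside the means.
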